#### **8.2.2.3. Guidance for Venous Thromboembolic Events**

In breast cancer, VTE has been identified as an adverse drug reaction for abemaciclib in combination with endocrine therapy (ET). In the randomized Phase 3 studies in participants with breast cancer who received abemaciclib in combination with ET, a greater number of participants experienced VTEs in the abemaciclib plus ET arms than in the placebo plus ET arm or ET alone arm. The majority of participants who experienced VTEs were treated with anticoagulants. In studies with single-agent abemaciclib use in the metastatic breast cancer population or other tumor types, including non-small cell lung cancer, no increased rates of VTEs were observed as

compared to the incidence of VTEs for these particular patient populations who were treated with other anticancer agents. At this time, the mechanism underlying the association between abemaciclib and the occurrence of VTEs is not known.

Monitor participants for signs and symptoms of deep vein thrombosis and pulmonary embolism and treat as medically appropriate. Dose modifications and management should follow the protocol guidance for non-hematological toxicities in Section 6.6.2.

#### **8.2.2.4. Guidance for Interstitial Lung Disease/Pneumonitis**

Interstitial lung disease (ILD)/pneumonitis has been identified as an adverse drug reaction for abemaciclib. The majority of events observed in clinical trials were Grade 1 or Grade 2 with serious cases and fatal events reported. Additional information is available in the IB.

Ask your participants to report any new or worsening pulmonary symptoms, such as dyspnea, cough, and fever, and investigate and treat as per your local clinical practice (including corticosteroids as appropriate). If ILD/pneumonitis is suspected, investigations may include imaging, such as high-resolution CT, bronchoalveolar lavage, and biopsy as clinically indicated. Refer to Section 6.6.2 for guidance on dose adjustments of abemaciclib for patients with ILD/pneumonitis (see Section 10.7, Appendix 7, for ILD/pneumonitis CTCAE grades). Discontinue abemaciclib in cases of severe (Grade 3 or 4) ILD/pneumonitis.

#### **8.2.3. Safety Surveillance**

The sponsor has robust safety surveillance processes based on recommendation made by Council for International Organizations of Medical Sciences (CIOMS) Working Group VI - Management of Safety Information from Clinical Trials Report. These processes are in line with FDA's expectations for Safety Assessment Committees and the European Medical Agency (EMA) expectations for monitoring safety in clinical trials.

Each investigational drug has a Developmental Safety Surveillance Team (DSST) which is responsible for monitoring the safety of participants and overseeing the evolving safety profile of investigational drugs. The DSST will review all available data including but not limited to clinical trial data (cumulative AE and SAE data and laboratory data), non-clinical data (toxicology studies), epidemiology studies and literature. The team will conduct real time review of all SAEs and other incoming expedited safety reports. The DSST is also responsible for review of accumulating safety data across all trials for the investigational drug. The DSST will meet in a timely manner at pre-defined intervals or on an ad-hoc basis as required.

The DSST is a multidisciplinary team which includes a physician/scientist who are well versed in Pharmacovigilance and with the therapeutic area for which the investigational drug is being developed. The roles and responsibilities of this team and the processes are clearly defined in Lilly's internal Standard Operating Procedures.

Each investigational drug has a Developmental Safety Management Team (DSMT) which is a cross-functional, multidisciplinary team and includes DSST members, study team physicians and other members depending on the necessity such as epidemiologist, clinical pharmacologist, toxicologist, statistician. The DSST and DSMT work together to review clinical data from the clinical trial.

The DSST can make recommendations to the DSMT in order to minimize risk to participants in clinical trials. Such recommendations will include (but are not limited to) changes to conduct of the trial, determination of new adverse drug reactions and determining if event(s) meets the criteria for expedited reporting to regulators (such as investigational new drug [IND] safety reports) and investigators.

In addition, each individual clinical trial study team has clearly defined processes to review all relevant safety data at cohort level and trial level in order to monitor safety of participants in clinical trials and enable trial level decisions such as dose escalation. More information about these processes can be found in Section 6.6 of the protocol.

Lilly Global Patient Safety has a robust process, for expedited communication of SAEs and suspected unexpected serious adverse reactions (SUSARs) per regulatory requirements and other important study information as needed. The protocol gives detailed information to study sites for collection and reporting of AEs and SAEs (see Sections 8.3 and 10.3, Appendix 3).

### **8.3. Adverse Events and Serious Adverse Events**

Lilly standards for reporting AEs are to be followed regardless if country regulatory requirements are less stringent. A clinical study AE is any untoward medical event associated with the use of a drug in humans, irrespective if the AE is considered related to abemaciclib.

Adverse events will be reported by the participant (or, when appropriate, by a caregiver, surrogate, or the participant's legally authorized representative).

The investigator and any qualified designees are responsible for detecting, documenting, and recording events that meet the definition of an AE or SAE and remain responsible for following up AEs that are serious, considered related to the study intervention or study procedures, or caused the participant to discontinue the study intervention (see Section 7).

The investigator will use CTCAE version 5.0 (NCI 2017) to assign AE severity grades.

Investigators are responsible for:

- monitoring the safety of participants in this study and for alerting Lilly or its designee to any event that seems unusual, even if this event may be considered an unanticipated benefit to the participant
- the appropriate medical care of participants during the study
- documenting their review of each laboratory safety report
- following, through an appropriate health care option, AEs that are serious or otherwise medically important, considered related to study intervention or the study, or that caused the participant to discontinue study intervention before completing the study. The participant should be followed until the event resolves, stabilizes with appropriate diagnostic evaluation, or is reasonably explained. Frequency of follow-up evaluation is left to the discretion of the investigator.

Lack of drug effect is not an AE in clinical studies, because the purpose of the clinical study is to establish treatment effect.

After the ICF is signed, study site personnel will record via CRF/electronic data entry/designated data transmission methods the occurrence and nature of each participant's preexisting conditions, including clinically significant signs and symptoms of the disease under treatment in the study.

In addition, study site personnel will record via CRF/electronic data entry/designated data transmission methods any change in the preexisting conditions and any new conditions as AEs. Investigators should record their assessment of the potential relatedness of each AE to study intervention via CRF/electronic data entry/designated data transmission methods.

The investigator will interpret and document whether or not an AE has a reasonable possibility of being related to study intervention or a study procedure, taking into account the disease, concomitant treatments, or pathologies. A "reasonable possibility" means that there is a cause and effect relationship between the study intervention and/or study procedure and the AE.

Planned surgeries and nonsurgical interventions should not be reported as AEs unless the underlying medical condition has worsened during the course of the study.

Study site personnel must report any dose modifications or treatment discontinuations that result from AEs to Lilly or its designee via CRF/electronic data entry/designated data transmission methods, clarifying, if possible, the circumstances leading to the dose modification or discontinuation of treatment

### **8.3.1. Time Period and Frequency for Collecting AE and SAE Information**

All SAEs will be collected from the signing of the ICF until participation in study has ended.

All AEs will be collected from the signing of the ICF until the short-term 30-day follow-up visit.

Adverse events that begin before the start of study intervention but after signing of the ICF will be recorded on the Adverse Event CRF. Although all AEs after signing the ICF are recorded by the site in the CRF/electronic data entry, SAE reporting to the sponsor begins after the participant has signed the ICF and has received study drug. However, if an SAE occurs after signing the ICF, but prior to receiving abemaciclib, it needs to be reported ONLY if it is considered reasonably possibly related to study procedures.

All SAEs will be recorded and reported to the sponsor or designee immediately and under no circumstance should this exceed 24 hours, as indicated in Section 10.3, Appendix 3. The investigator will submit any updated SAE data to the sponsor within 24 hours of it being available. Serious adverse events, including death, caused by disease progression should not be reported unless the investigator deems them to be possibly related to study intervention.

Investigators are not obligated to actively seek AEs or SAEs after conclusion of the study participation (the participant summary CRF has been completed). However, if the investigator learns of any SAE, including a death, at any time after a participant has been discharged from the study, and he/she considers the event to be reasonably related to the study intervention or study participation, the investigator must promptly notify the sponsor.

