Vital Signs		X	X	X	X	X	X	X		Perform prior to administering abemaciclib. Collect temperature, blood pressure, pulse oximetry, and pulse rate. Repeat if clinically indicated. Does not need to be repeated on Cycle 1 Day 1 if assessed at baseline $\le 3$ days prior to abemaciclib initiation.
ECOG Performance Status		X	X		X		X	X		Does not need to be repeated on Cycle 1 Day 1 if assessed at baseline $\le 3$ days prior to abemaciclib initiation.
Other Clinical Assessments										
12-Lead ECG	X						X			Single ECG performed locally. Participants must be supine for approximately 5 to 10 minutes before ECG collection and remain supine but awake during ECG collection. Repeat if clinically indicated.
AE Assessment	X				X		X	X		Collect continuously at every visit and throughout the study using CTCAE Version 5.0. See Section 8.3 for further details on AE and SAE reporting.

Screening, On-Treatment and Post-Treatment Schedule of Activities										
Study phases	Screening		On Treatment Cycle duration = 28 days				Post-Treatment Follow-up		Instructions	
	Baseline		Cycle 1		Cycle 2		Cycle 3 and subsequent	Short-Term Follow-Up a	Long-Term Follow-Up b	Procedures and disease assessments (tumor imaging) should be performed as per the schedule of activities, according to the calendar days, regardless of treatment delays.
Relative Day within Dosing Cycle & Visit Window ( $\pm n$ days)	$\le 28$	$\le 14$	D1 ( $\pm 3$ )	D15 ( $\pm 3$ )	D1 ( $\pm 3$ )	D15 ( $\pm 3$ )	D1 ( $\pm 3$ )	V801 (30 days $\pm 7$ )	V802-8XX (90 days $\pm 14$ )	
Laboratory Assessments										
Hematology		X	X	X	X	X	X	X		See Section 10.2, Appendix 2. Does not need to be repeated on Cycle 1 Day 1 if assessed at baseline $\le 3$ days prior to abemaciclib initiation. Repeat if clinically indicated.
Chemistry		X	X	X	X	X	X	X		See Section 10.2, Appendix 2. Does not need to be repeated on Cycle 1 Day 1 if assessed at baseline $\le 3$ days prior to abemaciclib initiation. Repeat if clinically indicated. Refer to Sections 8.2.2.1 and 10.5, Appendix 5, for hepatic monitoring.
PSA		X	X		X		X	X		See Section 10.2, Appendix 2.
Testosterone		X	X		X		X	X		See Section 10.2, Appendix 2.

Screening, On-Treatment and Post-Treatment Schedule of Activities										
Study phases	Screening		On Treatment Cycle duration = 28 days				Post-Treatment Follow-up		Instructions	

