Abbreviations: AE = adverse event; CNS = central nervous system; CT = computed tomography; CTC = circulating tumor cells; CTCAE = Common Terminology Criteria for Adverse Events (NCI 2017); D = day; ECG = electrocardiogram; ECOG = Eastern Cooperative Oncology Group (Oken et al. 1982); EORTC-QLQ-C30 = European Organization for the Research and Treatment of Cancer Quality of Life Questionnaire; FACT-GP5 = Functional Assessment of Cancer Therapy- General; MRI = magnetic resonance imaging; n = number; NRS = numeric rating scale; PD = pharmacodynamics; PGx = pharmacogenomics; PK = pharmacokinetics; PRO = patient-reported outcome; PRO-CTCAE = Patient-reported outcome Common Terminology Criteria for Adverse Events; PSA = prostate specific antigen; QoL = quality of life; SAE = serious adverse event; V = visit.

a Short-term follow-up begins when the participant and investigator agree that the participant will no longer continue study treatment and lasts approximately 30 days ( $\pm 7$  days).

b Long-term follow-up begins when the short-term follow-up period is completed and continues until the participant's death, loss to follow-up, or study withdrawal.

In all cases, no follow-up procedures will be performed for a participant who withdraws informed consent unless he has explicitly provided permission and consent.

Mobile healthcare service may be leveraged to collect and process lab samples in conjunction with a patient's visit, when deemed appropriate by the investigator and allowed by local laws and regulations.

Continued Access Schedule of Activities			
Study phase	Continued Access Treatment	Follow-up a	Instructions
	V501-V5XX	V901	
Procedure			
Abemaciclib	X		Orally twice daily on Days 1 through 28 of a 28-day cycle.
AE collection	X	X	
Assessments to be conducted at a minimum with each collection and dispensing study drug (every 28 days) from Visits 501-5XX. After V801, only SAEs that are related to study intervention or protocol procedure will be collected.
 
Frequency of evaluation, including efficacy assessments, is left to the judgement of the investigator based on standard of care.

Abbreviation: AE = adverse event; SAE = serious adverse event; V = visit.

a Continued access follow-up begins when the patient and the investigator agree that the patient will no longer continue abemaciclib in the continued access period and lasts approximately 30 days.

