6.11.2. Adverse Events

Adverse event verbatim text will be mapped by the sponsor or designee to corresponding terminology within the MedDRA. Severity grades will be assigned by the investigator using CTCAE version 5.0. Medical Dictionary for Regulatory Activities PTs, identified by Medical as clinically identical or synonymous, will be grouped together under a single, consolidated PT. For example, 'Neutropenia' and 'Neutrophil count decreased' will be reported as 'Neutropenia'. Adverse events will be reported according to PTs resulting from this process.

Preexisting conditions are defined as AEs that begin prior to the first dose of study drug.

A treatment-emergent adverse event (TEAE) is defined as any AE that begins between the day of first dose and 30 days after treatment discontinuation (or up to any time if serious and related to study treatment) or any preexisting condition that increases in CTCAE version 5.0 grade between the day of first dose and 30 days after treatment discontinuation (or up to any time if serious and related to study treatment).

The MedDRA Lowest-Level Term will be used for comparisons of preexisting conditions to on-treatment events in the treatment-emergent computation.

A serious adverse event (SAE) is any AE during this study that results in one of the following outcomes:

- death
- initial or prolonged inpatient hospitalization

- a life-threatening experience (ie, immediate risk of dying)
- persistent or significant disability/incapacity
- congenital anomaly/birth defect, and
- is considered significant by the investigator for any other reason.

Important medical events that may not result in death, be life-threatening, or require hospitalization may be considered SAEs when, based on appropriate medical judgment, they may jeopardize the patient and may require medical or surgical intervention to prevent one of the outcomes listed in this definition.

The following AE listings and summaries will be produced:

- Overview of TEAEs
- Summary of TEAEs by PT (all grade and Grade ≥ 3)
- Summary of TEAEs by System Organ Class (SOC) and PT (all grade and Grade ≥ 3)
- Summary of TEAEs by PT and maximum grade (1-5)
- List of SAEs
- Summary of SAEs by SOC and PT (all grade and grade ≥ 3), and
- Summary of AEs as reason for study treatment discontinuation by PT.

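### Non-serious AE collection ends at V801, which may fall on day 23, but the SAP counts TEAEs to day 30 after an undefined discontinuation date: a small gap of at most 7 days if the two clocks start together

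*Protocol*

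**What the plan says.** - **End of collection.** Protocol 8.3.1: "All AEs will be collected from the signing of the ICF until the short-term 30-day follow-up visit". For serious events the same section differs: "All SAEs will be collected from the signing of the ICF until participation in study has ended".
- **Timing of the visit.** The column header for V801 in Protocol 1.3 gives 30 days with a window of 7 days either way. Footnote a sets the starting point: "Short-term follow-up begins when the participant and investigator agree that the participant will no longer continue study treatment and lasts approximately 30 days", again ±7 days.
- **AE row of the schedule.** Protocol 1.3: "Collect continuously at every visit and throughout the study using CTCAE Version 5.0". The row then sends the reader to Section 8.3 for details.
- **Analysis window.** SAP 6.11.2 counts as treatment-emergent "any AE that begins between the day of first dose and 30 days after treatment discontinuation", and any pre-existing condition that increases in grade over the same period. The only extension beyond day 30 is "or up to any time if serious and related to study treatment".

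The SAP does not say whether treatment discontinuation is the last dose or the date of the decision. Neither document asks for a contact at day 30 after an early V801, and neither ends the TEAE window at V801.

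**The concern.** Collection stops at a visit that can move, while the analysis window stops on a fixed day. When the visit is early, the SAP defines as treatment-emergent some days on which the protocol no longer asks sites to record non-serious events. A late visit does not compensate: non-serious events that begin after day 30 are collected, but the SAP definition leaves them out.

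The safety profile is a secondary objective. The TEAE summaries (all grades, Grade 3 or higher, and those related to treatment) all use this definition. A reader would take them to cover 30 days after treatment for every patient, when actual coverage would depend on when each site scheduled V801.

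**Working it through.** This is date arithmetic. The plan states no figure of its own to reproduce.

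**Inputs**
- V801 day, counted from the agreed stop of treatment: 23 to 37, from 30 ± 7 (Protocol 1.3).
- End of the TEAE window: day 30 after treatment discontinuation (SAP 6.11.2).
- Lag: days from treatment discontinuation, in the SAP's sense, to the agreed stop. The documents do not give it. It is 0 if the SAP means the decision date. If the SAP means last dose, it is the time from last dose to decision. I take it as 0 or more and vary it.

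**Formula**

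Uncollected days = max(0, 30 − (lag + V801 day)).

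**Gap by V801 day and lag**

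| Lag (days) | V801 on day 23 | V801 on day 30 | V801 on day 37 |
|---|---|---|---|
| 0 | 30 − 23 = 7 | 0 | 0 |
| 3 | 30 − 26 = 4 | 0 | 0 |
| 7 | 30 − 30 = 0 | 0 | 0 |
| 14 or 28 | 0 | 0 | 0 |

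The ceiling is 7 days, or 7/30 = 23% of the post-treatment part of the window. With V801 on day 37 and no lag, 37 − 30 = 7 days of collected non-serious events fall outside the TEAE definition.

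**Typical size, assuming no lag and V801 spread evenly over days 23 to 37**
- Possible visit days: 37 − 23 + 1 = 15. Those before day 30: 7 (days 23 to 29), so 7/15 = 47% of patients.
- Gaps on those days: 7 + 6 + 5 + 4 + 3 + 2 + 1 = 28.
- Mean among patients seen early: 28/7 = 4 days.
- Mean over all patients: 28/15 = 1.9 days, or 1.9/30 = 6% of the post-treatment window.

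**Same even spread with a 3-day lag**
- Gaps 4 + 3 + 2 + 1 = 10, affecting 4/15 = 27% of patients; mean over all patients 10/15 = 0.7 days.

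**Against the whole TEAE window**
- The window opens at first dose. With two 28-day cycles on treatment (an illustration, not a figure from the plan) it lasts 56 + 30 = 86 days. The ceiling is then 7/86 = 8%, and the even-spread mean 1.9/86 = 2%.

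**The case against.** The strongest reply is that the two clocks are not the same. V801 is timed from the agreement to stop, and the SAP may be counting from last dose. Protocol 6.6 allows suspension for up to 28 days before permanent discontinuation is considered, so a lag of a week or more is plausible for patients who stop because of toxicity, and for them there is no gap. This stands. The 7 days are a ceiling under one reading, and the 47% needs both no lag and evenly spread visits. It does not remove the point, because the SAP leaves the date undefined and the gap is real wherever the dates coincide.

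A second reply is that the AE row of the schedule calls for continuous collection throughout the study. That row refers to Section 8.3, which sets the V801 cut-off. If the row is meant more broadly, the two protocol texts disagree and still need reconciling.

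Third, much is already protected. Serious events are collected after V801. Protocol 8.3 also has investigators follow events that are serious or otherwise medically important, related, or the cause of discontinuation until they resolve, stabilise or are explained, so such toxicity already present at V801 is not dropped. This stands and narrows the affected set to new non-serious events, and worsening pre-existing conditions, between V801 and day 30.

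A reader might also infer that laboratory and vital-sign results are cut short. The documents do not support that. SAP 6.11.4 summarises laboratory grades by cycle and by worst postbaseline grade over the whole study, and SAP 6.11.5 summarises vital signs by cycle. Neither uses a 30-day window, so a sample on day 23 contradicts nothing.

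**Conclusion.** The mismatch is real and minor. If the agreed stop and treatment discontinuation are the same date, up to 7 days of the TEAE window go uncollected for patients whose V801 precedes day 30. With evenly spread visits this averages 4 days among those patients and about 1.9 days over all patients. With a lag of 7 days or more the gap is 0. The documents give neither the lag nor the distribution of V801 dates, so these averages are illustrations.

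The direction is not in doubt: followed as written, the plan can only under-count non-serious TEAEs of late onset or late worsening. It would be tempting to say that every patient loses 23% of post-treatment follow-up, or that late toxicity in general is missed. The documents support neither: the first is a per-patient maximum under one reading of the dates, and the second ignores SAE collection and the follow-up of ongoing events. The number of events lost cannot be estimated from the documents. The safety tables are descriptive, and the response and time-to-event endpoints are untouched.

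**What to change.** 1. Define treatment discontinuation as a single date, last dose or decision date, and use it in both documents for the V801 clock and the TEAE window.
2. Reword Protocol 8.3.1 so that all AEs are collected *until V801 or 30 days after treatment discontinuation, whichever is later*, with a brief telephone AE check at day 30 when V801 takes place earlier. The uncollected part of the window then falls to 0 days.

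The cost is one sentence in the protocol, one definition shared by both documents, and an occasional telephone call. The ±7-day window for V801 can stay as it is.

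If the protocol is not to be amended, the fallback is in the SAP: for non-serious events, end the TEAE window at the earlier of V801 or day 30, and label the tables accordingly. That costs one sentence and makes the tables honest about their coverage, but it does not recover the missing days.
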